6.3 Study procedures

The intervention will be offered close to the patients home. Patients in the control arm are offered standard medical care according to the local protocols.

- ***Dietary Intake***

At discharge all patients will visit a dietary professional to assess their protein and caloric intake.

- ***Physical exercise therapy***

The physical exercise therapy program will start four weeks after hospital discharge for duration of 12 weeks. The intervention group is offered a supervised and personalized exercise program that is aimed at both cardiorespiratory fitness (aerobic training) and muscle strength (resistance training) (48), which is also considered feasible in patients receiving chemotherapy (30). The program is developed in a close collaboration between physiotherapists, exercise physiologists, revalidation specialists, and medical and surgical oncologists. For each patient, an intake or baseline exercise measurement (i.e. 6 minute walk test and muscle function tests) will be performed at their medical center. Subsequently, the program will be specified to each patient's personal preferences and physical fitness with their physiotherapists. Hereafter, patients will train twice a week for one hour under supervision of a physical therapist. Patients are offered the following program: muscle strength training for 30 minutes per session. One training session exists of a minimum of six exercises: 1. Vertical row (longissimus, biceps brachii, and rhomboideus); 2. Leg press (quadriceps, glutei, gastrocnemius); 3. Bench press (pectoralis major, triceps); 4. Pull over (pectoralis, triceps brachii, deltoideus,

trapezius); 5. Abdominal crunch (rectus abdominis); 6. Lunge (quadriceps, glutei, hamstrings). For each exercise 3 sets of 8-12 repetitions should be performed. The training load should be adjusted up wards if a patient can perform more than 12 repetitions, and lowered if a patient can perform less than 8 repetitions. Aerobic training will be performed for next 30 minutes. The intensity of the training should be adjusted according to the Borg scale of perceived exertion, resulting in an exercise intensity of around 14. The maximum experienced workload will be 50-80% of the patients maximal physical capacity. The heart rate should be between 60-90% of the maximum heart rate. The maximum heart rate is approximated by subtracting the patients age from 220 (30). Patients will be informed about and motivated to perform daily exercise according to the Dutch Consensus on Healthy Exercise (49).

- ***Solution focused (psycho)therapy***

Solution focused therapy has empirically been validated and shown successful in patients with chronic diseases (50). Furthermore, it has improved symptoms of fatigue in patient populations with somatic diseases, such as patients with inflammatory bowel disease, by our research group (23, 24). It was considered more feasible with fewer drop outs than problem solved therapy (24). Contrary to other forms of psychotherapy, solution focused therapy is goal-oriented, future-focused and focuses on solutions to patients' problems rather than on their problems. This approach assumes that everyone has some knowledge of what would make their life better, as well as some necessary coping skills. It is a short-term psychological intervention during which patients will be offered various interventions to channel their attention towards constructing solutions, including: goal setting, compliments, miracle questions, scaling questions, coping questions, and exception questions. The solution focused therapy will be offered in six sessions of one hour during twelve weeks and will be organised at the patients home following a similar structure as used by "Niertteams aan Huis".

6.4 Withdrawal of individual subjects

Subjects can leave the study at any time for any reason if they wish to do so without any consequences. The investigator can decide to withdraw a subject from the study for urgent medical reasons.

6.5 Replacement of individual subjects after withdrawal

Withdrawn subjects will not be replaced.

6.6 Follow-up of subjects withdrawn from treatment

Overall- and disease free survival will be assessed.

6.7 Premature termination of the study

Although we have currently no reason to believe that the intervention is too intensive for the patients to be included, the study will prematurely be terminated when the intervention seems to be unfeasible.

If the drop out of included patients exceeds the estimated dropout rate and inclusion of patients within the given study period will not be possible, the study will prematurely be terminated.

7. SAFETY REPORTING

7.1 Temporary halt for reasons of subject safety

In accordance to section 10, subsection 4, of the WMO, the sponsor will suspend the study if there is sufficient ground that continuation of the study will jeopardise subject health or safety. The sponsor will notify the accredited METC without undue delay of a temporary halt including the reason for such an action. The study will be suspended pending a further positive decision by the accredited METC. The investigator will take care that all subjects are kept informed.

7.2 AEs, SAEs and SUSARs

7.2.1 Adverse events (AEs)

Adverse events are defined as any undesirable experience occurring to a subject during the study, whether or not considered related to [the investigational product / trial procedure/ the experimental intervention]. All adverse events reported spontaneously by the subject or observed by the investigator or his staff will be recorded.

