Study design: In this multicentre randomized controlled trial, patients will randomly be assigned to the treatment (rehabilitation program) or control (usual care) group in the four participating centres. After hospital discharge, the treatment group will undergo a supervised, tailored exercise program aimed at both cardiorespiratory fitness (aerobic training) and muscle strength (resistance training) twice a week during twelve weeks. Furthermore, one hour solution focused therapy is offered every other week. The primary outcome will be MFI-General Fatigue, at 12 months after surgery. Secondary outcomes are quality of life, cardiopulmonary fitness, skeletal muscle mass and strength, distribution and intensity of physical activity, MFI-Physical Fatigue, MFI-Mental Fatigue, MFI-reduced activity and motivation, frailty, anxiety, depression, and body weight, and risk of malnutrition assessed preoperatively, at the start and end of the rehabilitation program and six and twelve months after surgery. Validated tests are used to assess these parameters. Furthermore, an effect of the intervention on overall survival will be investigated.

Study population: Adult HPB cancer patients undergoing surgical cancer resection in Erasmus MC (Rotterdam), AMC (Amsterdam), LUMC (Leiden), and UMCG (Groningen) will be included in this study.

Intervention (if applicable): rehabilitation program consisting of physical exercise therapy, psychotherapy and dietary consultation.

Main study parameters/endpoints: General fatigue, assessed with the Multidimensional Fatigue Inventory (MFI).

Nature and extent of the burden and risks associated with participation, benefit and group relatedness: None.

INTRODUCTION AND RATIONALE

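### Adverse event capture in 7.2.1 is passive and leaves the status and reporting route of the local therapists undefined, so non-serious training-related events can go unrecorded or be observed more often in one arm

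*Protocol*

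**What the plan says.** Section 7.2.1 defines adverse events broadly: "Adverse events are defined as any undesirable experience occurring to a subject during the study, whether or not considered related to" the intervention. It then fixes how they reach the record: "All adverse events reported spontaneously by the subject or observed by the investigator or his staff will be recorded". No solicited question is described there or elsewhere in section 7.

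Section 6.3 places the intervention outside the study centres: "The intervention will be offered close to the patients home". On exercise it says "The physical exercise therapy program will start four weeks after hospital discharge for duration of 12 weeks", and that "patients will train twice a week for one hour under supervision of a physical therapist". On psychotherapy it says "The solution focused therapy will be offered in six sessions of one hour during twelve weeks and will be organised at the patients home". Control patients receive standard medical care under local protocols.

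No section says whether these therapists belong to the investigator's staff, or asks them to record events or pass them on. Section 7.2.2 sets the deadlines for serious events from the sponsor's first knowledge, without saying how an event at a local practice becomes known to the sponsor. Section 7.5 marks the safety board as not applicable.

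**The concern.** The people best placed to see a training-related event are the therapists who supervise the sessions, and the capture rule does not say whether what they see counts. The rule therefore has two readings. Under one, their observations are lost unless the patient repeats them to the investigator. Under the other, one arm gains a layer of observation that the other lacks. Patients and therapists are unblinded (section 6.2), so allocation is known wherever an event is noticed or reported.

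What is at stake is the safety description of a supervised exercise programme that starts soon after major abdominal cancer surgery. A low count of non-serious events could mean a well-tolerated programme or events that were not passed on. A higher count than in controls could mean harm or closer observation. How adverse events are collected is a protocol matter, and 7.2.1 is where this protocol settles it, so the point is not one left to an analysis plan.

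**Working it through.** The protocol states no adverse event rate, detection rate or safety power, so there is no figure of its own to reproduce. The check sets the sections side by side and counts contacts.

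**Step 1: scheduled sessions per rehabilitation patient (6.3).**
- Exercise: 2 per week x 12 weeks = 24.
- Psychotherapy: 6.
- Total: 24 + 6 = 30 at full attendance. Programme sessions for controls: 0.

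**Step 2: where the study visits fall (6.3 and Appendix 2).**
- Training starts 4 weeks after discharge and runs to 4 + 12 = 16 weeks.
- T1 is at 2 weeks, before training. T2 is at 17 weeks, after it ends.
- T1.5, at 10 weeks, lies within training, but the schedule as shown marks only accelerometer tracking there.
- A patient who waits for a full assessment visit to mention an event from the first session would do so 17 - 4 = 13 weeks later.

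**Step 3: the two readings of the rule.**
- *Therapists are not staff.* An event seen at a session enters the record only if the patient volunteers it or trial staff see it for themselves. The consequence is missed events in the rehabilitation arm.
- *Therapists are staff.* Their observations are recorded, at up to 30 contacts that exist in one arm only. The consequence is unequal observation.

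The two consequences belong to different readings and should not be added together.

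**Step 4: illustration only.** With 154 patients at 1:1 (sections 2.4 and 6.2) there are 154 / 2 = 77 per arm. All event rates and capture probabilities below are assumptions.

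*Missed events.* Expected recorded = 77 x true rate x capture.
- True rate 5%: 77 x 0.05 = 3.9 patients with an event. Capture of 30% records 1.2, and capture of 80% records 3.1.
- True rate 2%, capture 30%: chance of recording at least one = 1 - (1 - 0.02 x 0.30)^77 = 0.37. With full capture it is 1 - 0.98^77 = 0.79.

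*Unequal observation.* With equal true risk in both arms, apparent excess = true risk x difference in capture. Control capture is set at 50%, rehabilitation capture at 70% to 90%.

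| True risk, both arms | Control patients recorded | Rehabilitation patients recorded | Apparent excess |
|---|---|---|---|
| 10% | about 4 | 5 to 7 | 2 to 4 points |
| 30% | about 12 | 16 to 21 | 6 to 12 points |
| 50% | about 19 | 27 to 35 | 10 to 20 points |

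With equal capture the excess is zero. The table shows the direction and how the size depends on the assumptions. It is not an estimate for this trial.

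**The case against.** The strongest reply is that nothing here is shown to happen. Patients may volunteer training-related events at any contact, the definition covers related and unrelated events alike, and therapists may in practice be treated as staff. Adverse events are not among the objectives or endpoints, and section 8 plans no between-arm test of them, so no planned efficacy conclusion is biased. Passive capture is also a recognised choice in a behavioural trial. All of this stands. It limits the point to a risk affecting the description of harm, but does not supply the missing status or reporting route.

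Several stronger readings might be inferred and are not supported:

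- *Training harm is in fact missed or miscounted.* The documents show that the rule allows this, not that it occurs. Deaths and hospitalisations are less likely to escape than non-serious events.
- *The contact imbalance is 34 against 4.* That would add the 30 sessions to the four visits T1 to T4. It leaves out standard-care contacts, at which events can also surface, and counts sessions as observation only if therapists are staff.
- *Monitoring covers capture in only 1 to 10% of patients.* That sample in the monitoring plan is a quality check on reporting, not the route by which events are recorded.
- *The termination rule lacks input.* Section 6.7 opens "Although we have currently no reason to believe that the intervention is too intensive for the patients to be included", and goes on to feasibility, drop-out and inclusion, which the monitoring plan follows through inclusion speed and drop-out.
- *Appendix 2 proves that no one asks.* It is an overview of measurements and is not exhaustive: as shown, it also omits the fatigue rating that decides randomisation. Its missing adverse event row agrees with 7.2.1 but proves nothing alone.
- *The Summary's risk statement is contradicted.* The Summary reads "Nature and extent of the burden and risks associated with participation, benefit and group relatedness: None". The exclusions in 2.3 are precautions, and 6.7 speaks of feasibility. Whether that wording is complete is a separate editorial matter.

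**Conclusion.** The point holds as a risk created by the wording of 7.2.1 combined with the delivery model in 6.3. Non-serious training-related events can go unrecorded if the local therapists are not staff, or be observed more often in the rehabilitation arm if they are. In both cases any description of harm by arm would be unreliable.

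The only size that the documents support is the count of up to 30 scheduled sessions per rehabilitation patient, with none for controls, and this assumes full attendance. The number of events missed, or the spurious difference between arms, cannot be derived from the protocol. The primary fatigue comparison is not affected. The change is a cheap improvement to safety ascertainment, not the correction of a faulty analysis.

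**What to change.** In section 7.2.1:

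1. Add one standard adverse event question, worded identically and asked in both arms at T1, T2, T3 and T4, and show it in Appendix 2.
2. State that any between-arm description of adverse events rests on those answers.
3. State whether the local physiotherapists and psychotherapists count as staff, and instruct them to report to the investigator any event seen at or after a session.
4. List session-detected events separately, so that they inform safety oversight without entering a comparison in which controls have no equivalent source.

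The visits already exist, so no extra visit or procedure is needed. The cost is a reporting instruction to therapists and more adverse events to process. One limit remains: T2 must cover the 17 - 2 = 15 weeks since T1 by recall. That recall period is the same in both arms, and the therapist reports in item 3 offset part of the loss for training-related events.

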7.2.2 Serious adverse events (SAEs)

A serious adverse event is any untoward medical occurrence or effect that

- results in death;
- is life threatening (at the time of the event);
- requires hospitalisation or prolongation of existing inpatients' hospitalisation;
- results in persistent or significant disability or incapacity;
- is a congenital anomaly or birth defect; or
- any other important medical event that did not result in any of the outcomes listed above due to medical or surgical intervention but could have been based upon appropriate judgement by the investigator.

An elective hospital admission will not be considered as a serious adverse event.

The sponsor will report the SAEs through the web portal *ToetsingOnline* to the accredited METC that approved the protocol, within 7 days of first knowledge for SAEs that result in death or are life threatening followed by a period of maximum of 8 days to complete the initial preliminary report. All other SAEs will be reported within a period of maximum 15 days after the sponsor has first knowledge of the serious adverse events.

7.3 Follow-up of adverse events

All AEs will be followed until they have abated, or until a stable situation has been reached. Depending on the event, follow up may require additional tests or medical procedures as indicated, and/or referral to the general physician or a medical specialist. SAEs need to be reported till end of study within the Netherlands, as defined in the protocol.

7.4 Follow-up of adverse events

All AEs will be followed until they have abated, or until a stable situation has been reached. Depending on the event, follow up may require additional tests or medical procedures as indicated, and/or referral to the general physician or a medical specialist. SAEs need to be reported till end of study within the Netherlands, as defined in the protocol

7.5 [Data Safety Monitoring Board (DSMB) / Safety Committee]

Not applicable.

8. STATISTICAL ANALYSIS

All data will be collected in an electronically secured safe environment for the participating centres (Open Clinica). Statistical analyses will be performed using SPSS statistical software. Data will be analysed on an intention to treat basis. Adjusted analysis with prognostic baseline characteristics (gender, age, education, marital status, disease stage, radicality of resection) will be performed. This results in increased statistical power, corrects for baseline differences (based on chance) and provides better individualized treatment effect estimates (51). Two-sided p-values <0.05 will be considered significant and clinically important changes will be estimated as effect sizes using Cohen's guidelines. An effect size of 0.2 will be considered as small, 0.5 as medium, and 0.8 as large.

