2.4 Sample size calculation

MFI-General fatigue is the primary outcome of the study. To detect a medium difference in MFI-General fatigue (Cohen's $d = 0.50$) with a power of 0.80 and alpha of 0.05 (two sided), both groups should consist of 64 patients. With an expected 20% drop out rate (25), a total of 154 patients are needed.

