6.2 Randomisation, blinding and treatment allocation

Patients will be included on the preoperative surgical outpatient department. If at hospital discharge patients score ≥ 4 on the fatigue NRS , they will randomly be assigned to the treatment (rehabilitation program) or control (standard care) group in a 1:1 ratio.

Centralized stratified permuted block randomization will be performed by the Clinical Trial Center using the online ALEA software. The sample will be stratified based on organ (liver, pancreas, biliary tract) and organisation (EMC, LUMC, AMC, UMCG). Block randomisation within each stratum will be performed using variable block sizes ranging from 2 to 4. Neither patients nor therapists will be blinded for the treatment group. All therapists will be blinded for the NRS fatigue score that will be obtained before the start of the rehabilitation program.

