8.1 Primary study parameter(s)

The primary end point is the MFI-General Fatigue score measured at 12 months after surgery as described earlier. Superiority of the intervention group versus the control group will be assessed using a Mann-Whitney U to test if the two independent samples come from the same distribution.

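### Organ and centre are stratified at randomisation but appear in neither the primary test nor the adjustment list; if they are prognostic, the test is conservative and modest power is lost

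*Protocol*

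**What the plan says.** **Design (section 6.2).** Allocation is "group in a 1:1 ratio". On the strata, the section states: "The sample will be stratified based on organ (liver, pancreas, biliary tract) and organisation (EMC, LUMC, AMC, UMCG". On the blocks, it adds this: "Block randomisation within each stratum will be performed using variable block sizes ranging from 2 to 4". Three organs by four centres make 12 strata.

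**Primary analysis (section 8.1).** "Superiority of the intervention group versus the control group will be assessed using a Mann-Whitney U". The sentence goes on to describe a comparison of two independent samples. It mentions no strata and no covariates.

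**Adjusted analysis (section 8).** "Adjusted analysis with prognostic baseline characteristics (gender, age, education, marital status, disease stage, radicality of resection) will be performed". The reason given is: "This results in increased statistical power, corrects for baseline differences (based on chance".

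**Secondary analysis (section 8.2).** A linear mixed model is planned for the longitudinal outcomes, with no covariates named.

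**Sample size (section 2.4).** The target effect is set out first: "To detect a medium difference in MFI-General fatigue (Cohen's $d = 0.50". The error rates and group size follow from there: "with a power of 0.80 and alpha of 0.05 (two sided), both groups should consist of 64 patients". The total is 154 after a 20% dropout allowance.

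**The concern.** Permuted blocks within strata force the arms to be nearly balanced on organ and centre. If these factors predict the outcome, that balance reduces the true sampling variance of the treatment contrast. A test that ignores the strata still counts the between-stratum variation as noise. It therefore rejects less often than its nominal level under the null, and it gives up part of the precision that the design has already bought.

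The covariate list does not repair this. It includes education and marital status but omits the two factors judged important enough to stratify on, although gaining power is one of the protocol's own reasons for adjusting. Because the protocol names both the test and the covariates, this is a stated choice and not a detail left open for a later analysis plan.

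The protocol gives some reason to think that the factors could matter. Its introduction quotes different one-year survival for primary hepatic and pancreatic cancer (39% and 24%), and section 6.3 lets control care follow local protocols, so the comparator may differ between centres. Neither is evidence about 12-month fatigue in resected patients.

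At stake is efficiency. The error is in the conservative direction.

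**Working it through.** **1. Reproduce the plan's figures.** For d = 0.50, power 0.80 and two-sided alpha 0.05, the exact two-sample t-test needs 63.8 per arm, so 64 (power 0.801). The stated total reproduces as 128 × 1.2 = 153.6, so 154. After 20% dropout, 154 × 0.8 = 123.2 patients are evaluable, or n = 61.6 per arm. At that size t-test power is 78.6% if the strata explain nothing.

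**2. Inputs.** The design and d come from sections 6.2 and 2.4. R², the share of 12-month outcome variance due to organ and centre together, is not in the protocol. I assume 5%, 10% and 15%, and also show 0%.

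**3. Formulas.** Take balance as complete and let k = 1/√(1 − R²), the factor by which the unstratified standard error overstates the true one.

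- True type I error of the unstratified test: 2 × [1 − Φ(1.96k)].
- Standardised effect: λ = 0.50 × √(61.6/2) × k = 2.775k.
- Power without the factors: the noncentral t with parameter λ must exceed the critical value multiplied by k (about 121 degrees of freedom, critical value 1.98).
- Power with the factors: the same λ, ordinary critical value, 5 fewer degrees of freedom (about 116).

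**4. Results (t-test scale).** The gain is the difference of the rounded powers.

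| R² | k | Type I error, factors ignored | λ | Power without | Power with | Gain (points) |
|---|---|---|---|---|---|---|
| 0 | 1.000 | 5.0% | 2.775 | 78.6% | 78.6% | 0 |
| 0.05 | 1.026 | 4.4% | 2.847 | 79.2% | 80.6% | 1.4 |
| 0.10 | 1.054 | 3.9% | 2.925 | 79.8% | 82.7% | 2.9 |
| 0.15 | 1.085 | 3.4% | 3.010 | 80.5% | 84.7% | 4.2 |

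Replacing the noncentral t by a normal approximation in the fifth column gives 79.3 / 79.9 / 80.6%, which changes nothing of substance. The first row shows that spending 5 degrees of freedom on useless terms costs practically no power.

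**5. Check with the actual test.** A simulation used 6,000 trials per setting, N = 154, 20% random dropout, 12 strata with blocks of 2 or 4, and the organ mix of section 2.1 (120 : 150 : 30). Equal centres and an SD of about 4 on the 4–20 scale were assumed.

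| R² | Mann-Whitney type I error | Mann-Whitney power | Linear model with organ and centre, power |
|---|---|---|---|
| 0 | 0.052 | 0.76 | 0.78 |
| 0.05 | 0.047 | 0.76 | 0.79 |
| 0.10 | 0.042 | 0.76 | 0.81 |
| 0.20 | 0.034 | 0.78 | 0.86 |

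The direction agrees. The power gap in this table is not purely a stratification effect: about one to two points are already present at R² = 0, where the only difference is rank test versus linear model. The table in step 4 isolates the stratification effect.

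**6. Stratum sizes.** Biliary patients are 30/300 = 10% of the expected mix. With equal centres (assumed), each biliary-by-centre cell has 154 × 0.10 / 4 ≈ 4 randomised patients, about 3 after dropout.

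**The case against.** The strongest reply is that stratified randomisation has already balanced the arms, so the unadjusted test is valid and needs no help. Validity stands: the error rate is at or below 5%, and no false-positive problem follows. But balance without matching analysis is exactly what makes the test conservative, so the reply does not answer the loss of power.

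A second reply is that nothing shows organ or centre to be prognostic for fatigue. This also stands, and it makes the whole consequence conditional.

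A third is that the statistical analysis plan could add the factors. It could, but the protocol names the test and the covariates, and a plan that followed it would carry the omission over.

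Some stronger readings are tempting and are not supported:

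- **That confidence intervals for the primary result are certainly too wide.** Section 8.1 specifies a Mann-Whitney test, which gives a p-value; it plans no standard error or interval. The effect is a conservative p-value, and only if R² is above zero.
- **That power rises by 2 to 6 points.** This comes from comparing 78.6%, the value at R² = 0, with 80.6–84.7% at R² of 5–15%. At the same R² the unstratified test also gains from the balance, so the difference is about 1 to 4 points.
- **That adjusting for disease stage without organ makes the stage effect uninterpretable.** The protocol does not say how stage is coded, and section 6.1.3 records both diagnosis and TNM stage, so organ-specific coding is possible. No objective estimates a stage effect, and its coding does not bias a randomised treatment comparison.

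**Conclusion.** The point holds as an inefficiency: the stated primary test and the named covariate list do not follow the stratified design, and the omission works against the protocol's own reason for adjusting. With organ and centre explaining an assumed 5–15% of the variance in 12-month MFI-General Fatigue, the nominal 5% test runs at about 4.4–3.4% and forgoes about 1.4–4.2 points of power at about 123 evaluable patients. If the factors explain nothing, nothing is lost.

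The omission itself is certain from the text. Its size is not, because it rests on the assumed R², on d = 0.50, on dropout of 20% that leaves the balance intact, and on t-test power as a stand-in for the rank test. The change should be made, but the trial's validity does not depend on it.

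**What to change.** - **Adjusted analysis (section 8) and linear mixed model (section 8.2):** add organ and centre as main effects, (3 − 1) + (4 − 1) = 5 degrees of freedom.
- **Primary comparison (section 8.1):** choose one of two options and state it before outcomes are compared by arm. Either use a linear model of the 12-month score with treatment, organ and centre as main effects, or keep a rank test in the form of a van Elteren test stratified by both factors, with a stated rule for pooling the sparse biliary-by-centre cells. Stratifying the rank test by organ alone would still leave centre out.

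Main effects are safer than 12 separate strata, given about 4 randomised patients per biliary-by-centre cell.

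**Cost:** no new data, since both factors are recorded at randomisation, and 5 of roughly 120 degrees of freedom. The model option also replaces the rank test as the primary method, which is a real protocol change and should be presented as one.
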